7.2.1 Analysis of Primary Efficacy Endpoint

7.2.1.1 Primary Analysis

ORR will be tested against the null ($\leq 30\%$) by 1-sided exact binomial test at 0.025 level. The estimated ORR (percent of subjects with a BOR of CR or PR), a 2-sided 95% exact confidence interval and the p-value will be provided. Number and percentage of subjects with BOR in each of the response categories (CR, PR, SD, PD, NED and UNK) will also be presented. All subjects in the analysis set will be included in the denominator in the calculation of the percentage for each response category or ORR. In other words, missing data will be imputed for the calculation of ORR by assuming that any subjects not exhibiting a response (CR or PR) are non-responders.

Best overall response (BOR) and ORR will be presented for the overall population. They will also be presented for the FL population, as well as other disease subtypes (MZL and SLL). For each disease subtype, the summary will be the same as that for the overall population except that the hypothesis test will not be performed.

ORR will be analysed for the subgroups provided in [Section 6.5](#). These subgroup analyses will also be performed similarly for FL subjects. A forest plot of ORR for different subgroups will also be provided.

Listings of data to support response assessment, including lesions with dimensions, liver/spleen assessments, bone marrow and B symptoms will be provided.

These analyses will be performed for the FAS and the EAS with FAS being the primary analysis set.

7.2.1.2 Sensitivity Analysis

The revised IWG criteria does not take lymphocytosis into account. As a sensitivity analysis, subjects that have a BOR of PR with lymphocytosis (PRwL) will be excluded from the numerator in the calculation of ORR. The denominator will be the same as that for the primary analysis of ORR.

PRwL is defined as:

- CR or PR per revised IWG criteria, and

- Lymphocytes meeting both of the following
 - $\geq 4,000/\mu\text{L}$
 - No decrease from baseline or decrease from baseline for less than 50%.

The lymphocyte count considered here should be within +/- 7 days of the IWG response assessment. If multiple lymphocyte counts are available, the one that is closest to the date of IWG response assessment will be used.

The IWG response used to determine PRwL will be based on the IRC assessment. Lymphocytes will be integrated into this algorithm programmatically. This analysis will be performed for SLL subjects in the FAS.

7.2.2 Analyses of Secondary Efficacy Endpoints

7.2.2.1 Progression Free Survival (PFS)

Censoring of PFS will be performed as detailed in Table 2 below. Note that progression may be documented based on scheduled or unscheduled disease status assessment, and that unscheduled disease status assessment may be included in calculating the gap between adequate disease status assessments.

PFS will be presented using the Kaplan-Meier method. A 2-sided 95% confidence interval for median PFS will be provided. PFS will be analysed for the FAS and the EAS with FAS being the primary analysis set. It will also be analysed for the follicular lymphoma population, as well as the other disease subtypes within the FAS.

Table 2: PFS and DOR censoring algorithm

Situation	Date of Event or Censoring	Outcome
No adequate baseline disease status assessment	Date of first dose	Censored
No adequate post-baseline disease status assessment unless death occurs prior to first post-baseline assessment	Date of first dose + 1	Censored
No documented progression or death before data cutoff	Date of last adequate disease status assessment	Censored

Situation	Date of Event or Censoring	Outcome
Documented progression with ≤ 1 missing scheduled disease status assessment before progression	Date of the earliest assessment that results in a finding of unequivocal progression	Event
Death before progression being documented with ≤ 1 missing scheduled disease status assessment before death	Date of death	Event
Documented progression or death following a long gap between adequate disease status assessments (e.g., 2 or more consecutive missed scheduled disease status assessments along with a gap of more than 6 months)	Date of last adequate disease status assessment before the gap	Censored
New anticancer treatment or procedure started before documented progression	Date of last adequate disease status assessment	Censored

Note: the first two rows are applicable to PFS only.

7.2.2.2 Duration of Response (DOR)

The censoring algorithm provided in [Table 2](#) above will also be used for DOR. Because DOR is only analysed for responders, the first two rows are not applicable. DOR will be presented using the Kaplan-Meier method. A 2-sided 95% confidence interval for median DOR will be provided. DOR will only be analysed for responders (CR or PR).

DOR will be analysed for the FAS and the EAS with FAS being the primary analysis set. It will be analysed for the FL population, as well as the other disease subtypes within the FAS. DOR will also be analysed for the following subgroups:

- FL subjects who received only 1 prior treatment of BR and is refractory
- Number of prior therapies (<3 or ≥ 3)
- Prior treatment with bendamustine (Yes or No)
- Refractory to bendamustine (Yes or No).

7.2.2.3 Overall Survival (OS)

Subjects who are last known to be alive will be censored at date of last contact. OS will be presented using the Kaplan-Meier method. A 2-sided 95% confidence interval for median OS (if reached) will be provided. OS will be analysed for the FAS and the EAS with FAS being the primary analysis set. It will also be analysed for the FL population, as well as the other disease subtypes within the FAS.

7.2.2.4 Time to Response (TTR)

TTR (continuous and categorical) will be descriptively summarized for responders (CR or PR) only. TTR will be analysed for the FAS and the EAS with FAS being the primary analysis set. It will also be analysed for the FL population, as well as the other disease subtypes within the FAS.

7.2.3 Analyses of Exploratory Efficacy Endpoint

7.2.3.1 LNR Rate

The estimated LNR rate will be provided together with a 2-sided 95% confidence interval. A waterfall plot of the best percent change in the SPD of nodal target lesions will also be provided. Only subjects with baseline and post-baseline nodal target lesion measurements will be included in the plot.

LNR rate will be analysed for the FAS and the EAS with FAS being the primary analysis set. It will also be analysed for the FL population, as well as the other disease subtypes within the FAS.

7.3 SAFETY ANALYSES

Unless otherwise specified, all safety analyses will be performed for the overall population as well as by different disease subtypes in the FAS.

7.3.1 Adverse Events

Adverse events (AEs) will be graded by the Investigator using the NCI-CTCAE version 4.03 where possible. If an AE is not included in the NCI-CTCAE version 4.03, the Investigator will grade the AE according to the algorithm outlined in Section 8.2.1.2 of the protocol. In the case of multiple AE occurrences of the same MedDRA PT within a subject, the most severe grade observed will be reported when displaying AEs by grade. AEs with a relationship to study drug flagged as 'None' or 'Remote' will be considered 'Not Treatment-Related'. AEs with a relationship of 'Possible', 'Probable', or 'Definite' will be considered 'Treatment-Related'. In the event that multiple AEs of the same MedDRA PT with different relationship assignments exist for a study subject, the most conservative relationship will be reported when displaying AEs by relationship.

Treatment-emergent adverse events (TEAE) will be tabulated. A TEAE is defined as any AE that emerges or worsens in the period from the first dose of study treatment to 30 days after the last dose of study treatment. The onset date of an adverse event will be compared to the first dose date and the last dose date plus 30 days to determine if the AE is treatment-emergent or not. If a partial date is adequate to determine when the onset date of an event occurred relative to first dose of study medication and the last dose date plus 30 days, then the partial date will be used. If a partial date does not provide enough information to determine the onset date relative to first dosing date and the last dose date plus 30 days, the adverse event will be assumed as treatment-emergent.

Adverse events (AEs) will be summarized by MedDRA SOC and PT, PT only, or SOC only. For summary tables by SOC and PT, SOC will be sorted alphabetically and PT will be sorted by decreasing frequency for the overall column within each SOC. For summary tables by PT only, PT will be sorted by decreasing frequency for the overall column.

Summaries (number and percentage of subjects) will be provided as follows:

- Overview of TEAEs
- TEAE by MedDRA SOC and PT
- TEAE by MedDRA SOC and PT – treatment-related
- TEAE by MedDRA SOC, PT for maximum grade ≥ 3
- TEAE by MedDRA SOC, PT for maximum grade ≥ 3 – treatment-related
- TEAE by MedDRA PT
- TEAE by MedDRA PT – treatment-related
- TEAE by MedDRA PT for PTs of grade ≥ 3
- TEAE by MedDRA SOC, PT and maximum grade
- TEAE by MedDRA SOC, PT and maximum grade – treatment-related
- Treatment-emergent SAEs by MedDRA SOC and PT
- Treatment-emergent SAEs by MedDRA SOC and PT – treatment-related
- Treatment-emergent SAEs by MedDRA PT
- Treatment-emergent SAEs by MedDRA PT – treatment-related
- TEAE by MedDRA SOC and PT resulting in death
- TEAE by MedDRA SOC and PT resulting in death – treatment-related
- TEAE by MedDRA SOC and PT resulting in study drug interruption
- TEAE by MedDRA SOC and PT resulting in study drug dose reduction
- TEAE by MedDRA SOC and PT resulting in study drug interruption or dose reduction
- TEAE by MedDRA SOC and PT resulting in study drug discontinuation
- TEAE by MedDRA SOC and PT resulting in study drug discontinuation – treatment-related

- Deaths on treatment (defined as on treatment or within 30 days of last dose)
- Deaths in follow-up (defined as deaths occurring >30 days after last dose)

Listings will be provided for the following:

- All Adverse Events
- Serious Adverse Events
- AEs resulting in study drug interruption
- AEs resulting in study drug reduction
- AEs resulting in study drug discontinuation
- Deaths on study (all-cause mortality, table structured as a listing)
- AEs resulting in death (table structured as a listing)

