- Cardiac: Subjects who develop new Grade 3 or higher cardiac events should have IPI-145 held until resolution of symptoms. This includes new Grade 3 QTcF prolongation only if >20 ms increase from Baseline. A new Grade 3 QTcF prolongation (>20 ms from baseline) requires triplicate ECGs with the average measurement used and the use of Fridericia's correction method (QTcF). For subjects with a right or left BBB, a new Grade 3 QTc prolongation is defined as an increase in QTcF of >100 ms from the pre-dose ECG to any post dose ECG as the QRS interval is prolonged at Baseline (by approximately 40 ms) in subjects with a BBB

Subjects requiring treatment interruption should be re-evaluated at least weekly until the toxicity improves to \leq Grade 1 or returns to Baseline level. IPI-145 dose will be restarted at doses described in [Table 7](#).

Treatment Interruption for Hematologic Toxicity

Worsening or transient Grade 3 or higher neutropenia, anemia, and/or thrombocytopenia caused by the subject's existing disease or by IPI-145 are to be expected. Blood counts should be monitored as described in the protocol with the frequency increased as clinically indicated in the setting of new or worsening Grade 3 or higher cytopenias. IPI-145 dosing may be interrupted at any time, at the discretion of the treating physician.

Treatment with IPI-145 should be interrupted for the following symptomatic hematologic toxicities:

- Grade 3 or higher febrile neutropenia
- Grade 3 or higher thrombocytopenia associated with Grade 2 or higher hemorrhage

**Protocol IPI-145-06
IPI-145****Verastem, Inc.**

The subject should be re-evaluated at least weekly until the toxicity improves to \leq Grade 1 or returns to Baseline.

A dose may be withheld up to 42 days for toxicity. Doses withheld for >42 days due to treatment-related toxicity will result in permanent discontinuation from treatment. Any subject who requires reduction to less than 10 mg BID due to repeat occurrence of the same treatment-related toxicity will be permanently discontinued from treatment. Any subject who requires reduction to less than 5 mg BID for different treatment-related toxicities will be permanently discontinued from study treatment. Dose levels are shown in [Table 7](#).

Table 7: IPI-145 Dosing Levels

Dose Level	Dose (mg)
1	25 BID
-1	15 BID
-2	10 BID
-3	5 BID

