4.4 TREATMENT DISCONTINUATION

A subject should be withdrawn from the study treatment if, in the opinion of the investigator, it is medically necessary, or if it is the wish of the subject. However, every effort should be made to keep the subject on study treatment. Subjects will be withdrawn from study treatment in case of any of the following reasons:

- An adverse event that requires permanent discontinuation of IPI-145
- Protocol-specified disease progression
- Subject death
- Noncompliance to protocol

- Investigator decision
- Subject becomes pregnant
- Termination of the study by sponsor
- Voluntary withdrawal from treatment by subject

In addition to the above reasons, other circumstances may necessitate discontinuation of a subject from the study treatment, as judged by the investigator or sponsor.

If a subject does not return for a scheduled visit, then every effort should be made to contact the subject. In any circumstance, every effort should be made to document subject outcome.

Adverse events (AEs) and SAEs leading to the discontinuation of a subject will be followed until resolution, resolution to baseline or until the event is considered chronic.

Subjects (including subjects that withdraw consent from study treatment but not overall study participation) must attend an End of Treatment Visit (EoT) (within 7 days following the decision to permanently discontinue study treatment) and a Safety Follow up Visit (30 +7 days from last dose of IPI-145) (Refer to Section 6.5.1 for further details). Subjects who have not withdrawn consent from overall study participation will enter long-term follow-up phase of the trial (see [Section 6.5.2](#)).

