8.2 PROCEDURES FOR ELICITING, RECORDING, AND REPORTING ADVERSE EVENTS

8.2.1 Eliciting and Recording Adverse Events

Subjects will be instructed to report all AEs and will be asked a general health status question at each study visit. All AEs will be recorded in the eCRF from the time of informed consent until 30 days after the last dose of study treatment for all subjects, excluding screen failures. All SAEs occurring from time of informed consent (for all subjects including screen failures) through 30 days after the last dose of study treatment will be processed as outlined in **Section 8.2.3**. An adverse event will be followed until it is either resolved, has returned to baseline, or is determined to be a stable or chronic condition.

At each required visit during the trial, all AEs that have occurred since the previous visit must be recorded. The Investigator or appropriate designee must determine if the adverse event is serious or non-serious.

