8.2.2.3 Persistent or Recurrent Adverse Events

A persistent AE is one that extends continuously, without resolution, between subject evaluation time points. Such events should only be recorded once on the AE eCRF (and SAE Report Form, if applicable). If a persistent AE changes in grade, it should be recorded as a new AE on the eCRF.

A recurrent AE is one that occurs and resolves between subject evaluation time points and subsequently recurs. All recurrent AEs should be recorded on the eCRF (and SAE Report Form, if applicable).

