7.1.6 Exposure to Study Drug

Extent of exposure to study drug will be characterized by:

- Total actual dose (mg) calculated as: Sum of all doses received throughout the study
- Duration (months) calculated as: (Last dose date – first dose date + 1) divided by 30.4375
- Dose Intensity (mg/day) calculated as: Total actual dose divided by duration in days
- Relative dose intensity (%) calculated as: Dose intensity divided by the intended dose intensity multiplied by 100. The intended dose intensity is 50 mg/day because the starting dose is 25 mg BID.
- Compliance rate (%) calculated as: total actual dose divided by the total prescribed dose multiplied by 100. The total prescribed dose is the sum of all doses prescribed throughout the study.

Total actual dose, duration (continuous and categorical), dose intensity, relative dose intensity and compliance rate will be descriptively summarized. The total number of cycles started (continuous and categorical) will also be provided. In addition, time on treatment phase, defined as time from first dose to date of decision to discontinue treatment will be provided.

Dose modification is characterized by dose reduction, dose interruption and dose increase. If the current non-zero prescribed dose level is lower (or higher) than the immediately preceding non-zero prescribed dose level, it is considered as a dose reduction (or increase), regardless of the dosing history prior to the immediately preceding dose. The number of dose reductions (1, 2, ≥ 3), dose interruptions (1, 2, ≥ 3) and dose increases (1, 2, ≥ 3) will be summarized. Dose reductions and interruptions due to adverse events as provided from the Active Treatment eCRF will be similarly summarized.

Exposure and dose modification will be summarized for the overall population as well as by different disease subtypes.

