7.3.2 Laboratory Data

Clinical laboratory assessments for this study include: hematology, blood chemistry including liver function tests (LFTs), coagulation, urinalysis and immunoglobulin. Values will be analysed after conversion into standard international units, where applicable. A complete listing of all laboratory parameters with normal ranges is included in [Appendix 1](#).

Applicable laboratory data will be graded according to NCI-CTCAE Version 4.03. Shift from baseline to maximum post-baseline grades will be tabulated for hematology, blood chemistry including liver function test (LFT), and coagulation.

Post-baseline lab values used in summary tables for shift in grades, and LFT elevations will include lab tests performed after the start of the first dose of study treatment, up to 30 days post last dose.

Laboratory parameters will be presented as follows:

- Shift from baseline to maximum post-baseline CTCAE grade for hematology laboratory parameters
- Shift from baseline to maximum post-baseline CTCAE grade for chemistry laboratory parameters
- Shift from baseline to maximum post-baseline CTCAE grade for coagulation laboratory parameters
- New grade ≥ 3 hematology laboratory parameters
- New grade ≥ 3 chemistry laboratory parameters
- By visit summary of change from baseline for immunoglobulin parameters

- Listing of subjects with AST or ALT >3xULN in combination with total bilirubin >2xULN. The elevations of ALT/AST and total bilirubin must occur within 2 days of each other.
- Listing of all laboratory values
- Listing of laboratory parameters with grade 3 or higher CTCAE grades.
- Listing of selected hematology laboratory parameters with CTCAE grades
- Listing of selected LFTs with CTCAE grades

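### When a toxicity hold is never followed by re-dosing, the last dose + 30 days cut-off can close the TEAE, grade-shift and LFT-elevation tables while the subject is still in the treatment phase

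*SAP*

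**What the plan says.** - **TEAE window.** SAP 7.3.1 and Protocol 9.5 cover events that emerge or worsen "in the period from the first dose of study treatment to 30 days after the last dose of study treatment". SAP 7.3.1 applies this by date: "The onset date of an adverse event will be compared to the first dose date and the last dose date plus 30 days".
- **Laboratory window.** For the grade-shift and LFT-elevation tables, SAP 7.3.2 uses "lab tests performed after the start of the first dose of study treatment, up to 30 days post last dose".
- **Hold.** Protocol 4.2: "A dose may be withheld up to 42 days for toxicity". Under this rule discontinuation becomes mandatory only beyond 42 days. Held subjects are seen at least weekly until the toxicity improves.
- **EoT.** Protocol 6.4 places the visit within 7 days of the decision to stop. Table 1 schedules AE/SAE review, liver function tests, chemistry and hematology at that visit.
- **Safety Follow-up.** Protocol 4.4 requires EoT "and a Safety Follow up Visit (30 +7 days from last dose of IPI-145").
- **Grade changes.** Protocol 8.2.2.3: "If a persistent AE changes in grade, it should be recorded as a new AE on the eCRF".
- **Treatment phase.** SAP 7.1.6 will report "time on treatment phase, defined as time from first dose to date of decision to discontinue treatment".
- **AE collection.** Protocol 8.2.1: "All AEs will be recorded in the eCRF from the time of informed consent until 30 days after the last dose of study treatment". The same section also wants events since the last visit recorded at every required visit, and Table 1 footnote p runs collection to the post-treatment visit.
- **Deaths.** SAP 7.3.1 has one category for deaths while on treatment or up to 30 days from the last dose, and another for deaths more than 30 days after it.

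Neither document says how the 30-day limit applies to a hold that ends in discontinuation without another dose.

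**The concern.** The safety tables count from the last dose, while the treatment phase and the EoT visit count from the decision to stop. For most subjects the two dates are close. They separate when drug is held for a toxicity that does not resolve. The last dose then lies weeks back, the 30 days run out during the hold, and the subject has not yet been declared off treatment.

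The classification also depends on what happens afterwards. A held Grade 3 event that becomes Grade 4 on day 35 is a new record with onset on day 35. If the subject is re-dosed by day 42, the last-dose date moves forward and the record is a TEAE. If not, the identical record is not a TEAE. The subjects who lose coverage are those whose toxicity persisted. Safety is a secondary endpoint of a single-arm trial, so no control arm would reveal an undercount.

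**Working it through.** No figure in the plan needs reproducing; the check is date arithmetic. Day 0 is the last dose taken.

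**Inputs**
- TEAE window and shift/LFT laboratory window close: day 30 (SAP 7.3.1, 7.3.2; Protocol 9.5)
- Longest hold: day 42, so discontinuation under this rule comes on day 43 at the earliest (Protocol 4.2)
- EoT: decision day D to D + 7 (Protocol 6.4)
- Safety Follow-up: days 30 to 37 (Protocol 4.4, 6.5.1)

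**Full terminal hold**
- Hold days outside the window: 42 − 30 = 12, that is 12/42 = 29% of the hold.
- EoT: day 43 to 43 + 7 = 50, which is 43 − 30 = 13 to 50 − 30 = 20 days after the window closes.
- Weekly re-evaluations counted from day 0 include days 35 and 42; both are outside.
- Safety Follow-up on days 30-37 precedes EoT on days 43-50.

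**Earlier decisions.** EoT is certain to be inside only if D + 7 ≤ 30, that is D ≤ 23. It is certain to be outside if D > 30.

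| Decision day D | EoT days | Position relative to day 30 |
|---|---|---|
| 23 or earlier | up to 30 | always inside |
| 24 to 30 | 24 to 37 | either side |
| 31 or later | 31 onward | always outside |
| 43 (hold limit passed) | 43 to 50 | outside by 13 to 20 days |

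If dosing resumes by day 42, the last-dose date moves forward and the whole hold is inside the window.

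**What is left out, by table**
- TEAE, maximum-grade and TEAE-death tables: records with onset after day 30, including worsenings entered as new records.
- Grade-shift and LFT-elevation tables: values after day 30, including EoT. Under the 14-day exemption in Table 1 footnote s, a value from day 29 or 30 could stand in for an EoT on day 43 or 44 (43 − 14 = 29; 44 − 14 = 30), but not for a later EoT.
- Death tables: a death on day 36, with no decision yet made, is on treatment and also more than 30 days after the last dose, so it meets both definitions. If the fatal event began after day 30, it is not a TEAE resulting in death.

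**The case against.** The strongest reply is that the protocol and the SAP agree on last dose + 30 days, and that this is generous for the drug. At the mean half-life of 4.5 hours given in Protocol 1.3.3.2, 30 days is 30 × 24 / 4.5 = 160 half-lives. An event first seen after day 30 off drug may not be drug toxicity. This stands against any claim of a demonstrated downward bias. It does not explain why the same event should count or not according to later re-dosing, nor why assessments scheduled at EoT should miss the tables. The 42-day allowance itself anticipates related toxicity that lasts beyond 30 days.

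A reader might infer more than the documents support:
- *That the held toxicity disappears from the tables.* It began on drug, so it is a TEAE at its grade up to day 30 and is eligible for the interruption and discontinuation tables.
- *That the data are lost.* The AE, SAE, death and laboratory listings carry no 30-day limit. Related SAEs stay reportable after the collection period (Protocol 8.2.3.1).
- *That AE recording simply stops on day 30.* Protocol 6.3.7 and one sentence of 8.2.1 say so, but the EoT column of Table 1, footnote p and another sentence of 8.2.1 point the other way. This is an inconsistency, not a settled loss.
- *That every laboratory table is cut.* The limit is written for the shift and LFT-elevation tables. The immunoglobulin by-visit summary has no stated limit, and the new Grade ≥3 tables are not expressly covered.
- *That sites must hold the Safety Follow-up visit first.* During an open hold a site does not know that the last dose has been taken, so this is partly an ambiguity of wording.

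**Conclusion.** The gap is real but narrow. It concerns subjects who are held for toxicity, are never re-dosed, and are discontinued late: EoT may fall outside the window for decisions on days 24-30 and always does from day 31. For them, new onsets and worsenings after day 30 leave the TEAE-based tables, and late-hold and EoT values leave the shift and LFT-elevation tables, although SAP 7.1.6 still counts the time before the decision as treatment phase. After a full terminal hold, 12 hold days are uncovered and EoT is 13 to 20 days late.

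The documents do not give the number of subjects affected. One might assume that 5-15% of 120, or 6-18 subjects, end treatment from a hold longer than 30 days. Nothing in the documents anchors that rate, and it would count long holds, not subjects with a new or worse event after day 30, who must be fewer. The 73% (11 of 15) with related Grade ≥3 events at 25 mg BID in the Phase 1 iNHL subjects says nothing about hold length. The effect is probably small. The change is worth making because the rule is inconsistent and the correction is cheap. The dates assume that day 0 is the last dose actually taken and that visits fall within their stated windows.

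**What to change.** 1. In SAP 7.3.1 and 7.3.2 and Protocol 9.5, end the TEAE window and the shift/LFT laboratory window at the later of last dose + 30 days and the EoT visit. State a substitute date where no EoT visit takes place: the decision date that SAP 7.1.6 already uses or, for a subject who dies before any decision, the date of death.
2. In SAP 7.3.1, make the two death categories mutually exclusive on that same cut-off.
3. In SAP 7.3.2, say whether the new Grade ≥3 tables follow the window.
4. Reconcile the AE-collection wording (Protocol 6.3.7, 8.2.1, Table 1 with footnotes p and t) with the hold provision, and likewise the order of the EoT and Safety Follow-up visits (Protocol 4.4, 6.4, 6.5.1). No hold or dosing rule needs to change.

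The cost is SAP text plus a protocol wording amendment that has to reach about 100 sites; no visit is added. A few more off-drug events will count as treatment-emergent, so AE rates become slightly less favourable, and the window length will vary a little between subjects. The last dose + 30 days version can be kept as a supportive summary.

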8.1.1 Adverse Event

Adverse event (AE) is any untoward medical occurrence associated with the use of a drug or with study participation, regardless of the relationship of the occurrence to IPI-145 or study protocol. An AE can be any unfavorable and unintended sign (including an abnormal laboratory finding), symptom or disease temporally associated with the use of the drug, whether or not considered related to the drug. An adverse event can arise from any use of the drug, and from any route of administration, formulation or dose, including an overdose.

Medical conditions present prior to the initiation of the study, as well as ongoing changes in laboratory values/conditions that are being treated at baseline, will be captured as an AE if the condition worsens.

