9.5 SAFETY ANALYSES

The FAS will be the primary analysis set for safety evaluation. Safety will be assessed by AEs, ECG and laboratory test measurements.

AEs will be coded using the Medical Dictionary for Regulatory Activities (MedDRA) version 16.1 or higher and graded according to NCI-CTCAE Version 4.03. If the AE is not included in the NCI-CTCAE Version 4.03, the Investigator will assign a grade according to [Section 8.2.1](#).

The focus of AE summaries will be on TEAEs. A TEAE is defined as any AE that emerges or worsens in the period from the first dose of study treatment to 30 days after the last dose of study treatment. AEs will be summarized by the frequency of subjects experiencing TEAEs by MedDRA system organ classes (SOC) and preferred terms (PT). Separate tabulations will also be

produced for drug-related AEs, SAEs, AEs that led to treatment discontinuation, and AEs of at least Grade 3 severity.

ECG measurements will be tabulated for changes over time on study.

Laboratory parameters will be summarized for changes over time by descriptive statistics, and laboratory values that are of Grade 3 severity or greater will be tabulated and listed on an individual subject basis.

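### SAP 7.3.1 flags treatment-emergent AEs by onset date with no grade comparison, while the protocol opens a new AE record at every grade change, so some AEs present before first dose are flagged contrary to the SAP's own definition

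*SAP*

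**What the plan says.** SAP 7.3.1 gives the definition: "A TEAE is defined as any AE that emerges or worsens in the period from the first dose of study treatment". The window closes 30 days after the final dose. Protocol 9.5 defines a TEAE in the same terms. SAP 7.3.1 then says how the flag is set: "The onset date of an adverse event will be compared to the first dose date and the last dose date plus 30 days". Where a partial date cannot place the onset, "the adverse event will be assumed as treatment-emergent". The section has no step that compares a record's grade with an earlier grade.

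Three protocol rules decide which records this step meets:

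- Section 8.2.2.3: "If a persistent AE changes in grade, it should be recorded as a new AE on the eCRF". The rule is not limited to increases.
- Section 8.2.1: "All AEs will be recorded in the eCRF from the time of informed consent until 30 days after the last dose of study treatment". Screening runs from Day -30 to Day -1 (Table 1), so AEs with onset before first dose will be in the database.
- Section 8.1.1: a medical condition present before the study "will be captured as an AE if the condition worsens". This keeps stable medical history out of the AE data. It does not cover an AE that first appears between consent and first dose.

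**The concern.** The definition depends on direction: the event must be new or worse. The working step depends only on date. The two agree only if every record with a post-dose onset is a new or worsened event, and the protocol's recording rule breaks that condition, because an improving AE also produces a new record.

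At stake is the accuracy of the TEAE tables by preferred term and by grade. The trial has one arm, so no control group carries the same misclassification for comparison. SAP 7.3 also produces the safety tables by disease subtype, where denominators are small and one misflagged subject shows more.

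**Working it through.** The plan states no figure to reproduce, so the check applies the SAP's date step and the SAP's definition to the same constructed records.

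**Set-up.** First dose is Day 1 and last dose Day 100, so the window runs from Day 1 to Day 100 + 30 = Day 130. Screening AEs start on Day -10. The documents do not say which onset date a grade-change record carries, so both possibilities are shown.

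| Case | Definition (emerges or worsens) | Date step, record dated at the change | Date step, original onset kept |
|---|---|---|---|
| Screening Grade 2, unchanged | Not a TEAE | Not a TEAE | Not a TEAE |
| Screening Grade 3, Grade 2 on Day 8 | Not a TEAE | **TEAE, Grade 2** | Not a TEAE |
| Screening Grade 4, Grade 3 on Day 8 | Not a TEAE | **TEAE, Grade 3** | Not a TEAE |
| Screening Grade 1, Grade 3 on Day 8 | TEAE, Grade 3 | TEAE, Grade 3 | **Not a TEAE** |
| New Grade 3 on Day 20, Grade 1 on Day 40 | TEAE, maximum Grade 3 | TEAE, maximum Grade 3 | TEAE, maximum Grade 3 |

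Bold marks disagreement with the definition. With records dated at the change, the date step fails on the improving cases. With the original onset kept, it fails on the worsening case. Neither convention makes the date step reproduce the definition. The SAP rule of showing the most severe grade per preferred term does not help: it picks the grade to display and does not remove a wrong flag.

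**Which comparator to use.** Take a screening AE that is Grade 3, falls to Grade 1 before first dose, and rises to Grade 2 on drug. It has worsened during treatment.

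- Against the highest pre-dose grade: 2 > 3 is false, so the event would be dropped.
- Against the grade at first dose: 2 > 1 is true, so it is kept.

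The grade at first dose is therefore the right comparator. It also matches SAP 6.7, which takes baseline as the last value before first dosing.

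**Size.** The documents give no rate for such events. Assume that *n* subjects have an affected record and no genuine TEAE of the same preferred term. The inflation of that term is then n / N:

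- n = 1, N = 120: 1/120 = 0.8 percentage points
- n = 6, N = 120: 6/120 = 5.0 percentage points
- n = 1 among the planned non-FL subjects, N = 120 - 80 = 40: 1/40 = 2.5 percentage points

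The upper figure requires all six subjects to share one preferred term. The range of 1 to 6 is an assumption and the true count could be lower.

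**The case against.** **The definition governs, and the date sentence only places a record in the dosing window.** On that view an improving record fails the definition and the SAP merely leaves an exception unsaid. This is a fair reading of intent. But the SAP presents the date comparison as the way to decide whether an AE is treatment-emergent, and it gives neither a grade step nor a comparator. A programmer who follows the text sets the wrong flag. One who adds a grade check has to invent the comparator, and the choice matters, as shown above.

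**The onset date of the new record is not documented.** This stands as a limit on which error occurs. It does not rescue the rule, because the other convention misses true worsening.

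**Over-inclusion is conservative and is already the SAP's choice for unresolved dates.** Over-counting does not hide harm, which keeps the point modest. That default, however, deals with dates that cannot be settled; in the cases above the dates are known.

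**Few subjects qualify.** This also stands. Monitoring for AEs starts after medical history is taken (protocol 6.3.7), stable pre-existing conditions are not AEs, and the exclusion criteria remove ongoing systemic infections and severe uncontrolled conditions. An event that began before any drug was taken should usually be judged unrelated on the temporal criterion in protocol 8.2.1.1, so the treatment-related tables should be little affected.

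A reader might infer more than the documents support:

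- *That the rule always inflates TEAE counts.* It does so only if records are dated at the grade change; otherwise it under-counts.
- *That treatment-emergent SAE counts are inflated by seriousness flags passing to the new record.* No text says that such flags carry over.
- *That the trial's whole safety description is compromised.* The SAP also has AE listings, tables of deaths, laboratory shifts from baseline with new Grade ≥3 values, and ECG change from baseline. These do not depend on the TEAE flag.

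**Conclusion.** The point holds in a limited form. The SAP's working step does not carry out its own TEAE definition once combined with the protocol's rule on grade changes. It affects AEs that start between consent and first dose, persist past first dose and then change grade. AEs that begin on treatment and later improve add nothing to subject-level counts, because they are already TEAEs.

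If grade-change records are dated at the change, improving events become false TEAEs, some of them Grade ≥3. If the original onset is kept, worsening events are lost. The effect falls on preferred-term and Grade ≥3 counts: 0.8 percentage points per affected subject out of 120, and more within the smaller subtypes. The overall TEAE rate should hardly change, and efficacy is untouched. How many subjects are affected cannot be determined from the documents. The correction is worth making because the stated rule gives a wrong flag and the remedy is cheap.

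**What to change.** Add to SAP 7.3.1:

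1. A record that continues an AE ongoing at first dose (same subject and preferred term, no resolution between records) is treatment-emergent only if its grade exceeds the grade at first dose, meaning the last grade before dosing, in line with SAP 6.7.
2. A record opened because of a grade change is dated at the change.
3. The onset-date rule stays for all other records, including events that resolved and recurred. The existing default to treatment-emergent stays where partial dates cannot settle the question.

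Applied to the table in the working, this clears the two improving cases and leaves the worsening and new events flagged. One consequence should be accepted openly: an AE that is Grade 3 at first dose, falls to Grade 2 on drug and returns to Grade 3 without resolving is not flagged, because it never exceeds its grade at first dose. It still appears in the AE listing.

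The cost is a few SAP sentences and a small programming step to link records of one event. No new assessments are needed. Because the documents do not show the eCRF completion instructions, the sponsor should confirm that sites enter the date of the change; if they do not, those dates would have to be checked before the flag is derived.
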